3.6.3.1 Selected Adverse Events

The following summary tables will be produced for the Period 1 (Safety Analysis Set) and 12-month LEM exposure (On-Treatment Safety Analysis Set) separately.

The following significant AEs will be summarized by SOC and PT:

- Cataplexy
- Potential cataplexy
- Falls
- Seizures
- Abuse liability events

Cataplexy includes the TEAEs with MedDRA PT of cataplexy, and drop attack.

Cataplexy and potential cataplexy includes the TEAEs with MedDRA PT listed in [Appendix 2](#) plus all events that have been flagged by investigator as potential event of cataplexy in the eCRF.

Falls includes the TEAEs with MedDRA PT of “fall” only.

Seizure includes TEAEs with MedDRA PTs belonging to MedDRA Standardized Queries (SMQ) of “Convulsions” (Narrow Terms).

Abuse liability events include TEAEs with MedDRA PT listed in [Appendix 3](#).

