9.2.3 Safety

To allow for a long-term safety evaluation, the present study will take place over a 12-month interval during which study drug will be taken daily by subjects, within 5 minutes before the subject intends to sleep.

To allow for correlation of plasma drug levels with safety, population PK-safety modelling will be conducted.

ADJUDICATION COMMITTEE (REVISED PER AMENDMENT 03)

An independent Adjudication Committee will be employed at intervals to review, in a blinded manner, AEs that could potentially be considered cataplexy or seizure. A set of preferred terms constituting a customized Medical Dictionary for Regulatory Activities (MedDRA) query for cataplexy or seizure will be used to identify events for adjudication (including cataplexy, muscle fatigue, muscular weakness, muscle tone disorder, hypotonia, drop attacks, slurred speech, diplopia, falls, convulsions [SMQ narrow and broad], atypical migraine, loss of consciousness, decreased consciousness, myoclonus, syncope, transient global amnesia, lipothymia [faintness] and transient ischemic attack). To assist in the preparation of narratives about such events and to support the committee's adjudication process, investigators and site staff will be instructed to query subjects who report any of the above events for supplemental information using a questionnaire for events potentially related to cataplexy and the serious adverse event (SAE) form for any of the above events considered serious. (revised per Amendment 03)

DATA SAFETY MONITORING BOARD (REVISED PER AMENDMENT 03)

An independent Data Safety Monitoring Board (DSMB) will convene at regular intervals to monitor the overall safety of the study and to make recommendations to the sponsor related to study safety as appropriate. The DSMB will be asked to review the cumulative safety data up to the date identified to make a determination of whether the trial is safe to proceed unchanged or to provide recommendations to the sponsor as to how to proceed. The study will proceed, including randomization of additional subjects, during DSMB safety reviews. Details will be provided in the DSMB Charter. (revised per Amendment 03)

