9.4.4 Selection of Doses in the Study

In Study 201, all doses studied met the 1st primary objective of balancing significant efficacy as measured by change from baseline in SE with sufficient safety measured by subjective sleepiness reported on the KSS. The 2nd primary objective was also achieved, as there were no significant increases in the KSS at 1 hour after waketime at the end of treatment. However, there were small dose-related increases in the KSS at both the beginning and end of treatment, and the rate of AEs of somnolence also increased with increasing dose level.

In Study 201, lemborexant 5 and 10 mg showed significant efficacy measured by sSE, as well as decreases in sSOL. These effects were maintained across the 15-day treatment period. For sleep maintenance, lemborexant 10 mg showed significant decreases, and while the magnitude of decreases in sWASO was less for 5 mg, there was a significant proportion of subjects whose sWASO decreased substantially, providing evidence for clinical benefit of 5 mg on sleep maintenance as well.

Because of the observed dose-related increases in subjective sleepiness and AEs of somnolence in Study 201, Study 107 was conducted to obtain additional information about the risk of clinically meaningful morning residual sleepiness. The study assessed average sleep latency on the M-MSLT after a single dose of LEM5 or LEM10 versus PBO. The results indicated that the pre-specified threshold for a clinically meaningful decrease in average sleep latency was not met by either the 5 mg or 10 mg dose level of lemborexant, supporting their use in the Phase 3 clinical trials. Taken together with the efficacy and safety results for LEM5 and LEM10 in the Phase 2 study, these dose levels were selected for the current study.

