The number (percentage) of subjects with TEAEs will also be summarized by maximum severity (mild, moderate, or severe).

The number (percentage) of subjects with TEAEs will also be summarized by relationship to study drug (Yes [related] and No [not related]). Treatment-related TEAEs include those events considered by the investigator to be related to study treatment.

The number (percentage) of subjects with treatment-emergent SAEs will be summarized by MedDRA SOC and PT for each treatment group. A subject data listing of all SAEs will be provided.

The number (percentage) of subjects with TEAEs leading to discontinuation from study drug will be summarized by MedDRA SOC and PT for each treatment group. A subject data listing of all AEs leading to discontinuation from study drug will be provided.

The number (percentage) of subjects with TEAEs of cataplexy or other events that are characterized according to the customized MedDRA query PT as cataplexy-related events, as well as somnolence and related events, and drug abuse liability will be summarized separately. The number of adjudicated events based on the report of the Adjudication Committee will also reported separately.

Customized MedDRA Queries (CMQ) for AEs that could potentially be considered cataplexy or seizure, somnolence, and related events, and preferred terms related to drug abuse liability, will be summarized. The results of the deliberation of the Adjudication Committee will be reported separately. (revised per Amendment 03)

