Appendix 2 List of Potential Cataplexy Events

Code	Preferred Term
10007737	Cataplexy
10009346	Clonus
10050093	Consciousness fluctuating
10012373	Depressed level of consciousness
10013036	Diplopia
10076060	Eyelid myoclonus
10078509	Heteronymous diplopia
10078508	Homonymous diplopia
10021118	Hypotonia
10024855	Loss of consciousness
10049565	Muscle fatigue
10072889	Muscle tone disorder
10028372	Muscular weakness
10028622	Myoclonus
10053854	Opsoclonus myoclonus
10036653	Presyncope
10050496	Reversible ischaemic neurological deficit
10071299	Slow speech
10042772	Syncope
10044380	Transient global amnesia
10044390	Transient ischaemic attack
10013887	Dysarthria
10033799	Paralysis
10009192	Circulatory collapse
10015995	Eyelid ptosis

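### SAP 3.6.3.1 leaves drop attack out of the broader cataplexy group and omits the somnolence summary that the protocol requires

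*SAP*

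**What the plan says.** **SAP groups.** SAP Section 3.6.3.1 lists five groups of selected adverse events: cataplexy, potential cataplexy, falls, seizures and abuse liability. The narrow cataplexy rule is "Cataplexy includes the TEAEs with MedDRA PT of cataplexy, and drop attack". The broader rule begins "Cataplexy and potential cataplexy includes the TEAEs with MedDRA PT listed in" Appendix 2 and continues "plus all events that have been flagged by investigator as potential event of cataplexy in the eCRF". Appendix 2, headed "List of Potential Cataplexy Events", holds 25 preferred terms. The seizure group is limited to the narrow terms of the Convulsions SMQ. No somnolence group or term list is defined in Section 3.6.3.1 or elsewhere in the SAP.

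**Protocol query.** Section 9.2.3 and the synopsis describe a customised MedDRA query for cataplexy or seizure, used to select events for adjudication. Its 18 items begin "cataplexy, muscle fatigue, muscular weakness, muscle tone disorder, hypotonia, drop attacks, slurred speech, diplopia, falls, convulsions [SMQ narrow and broad".

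**Protocol summaries.** Section 9.7.1.8.2 requires tables of cataplexy-related events, "as well as somnolence and related events, and drug abuse liability will be summarized separately". The same section and the synopsis (Safety Analyses) add that the customised queries, for cataplexy or seizure and for somnolence, will be summarised.

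**Declared changes.** SAP Section 5 names two major changes: extra MMRM time points and the On-Treatment Safety Analysis Set. SAP Table 1 records that the potential-cataplexy summary and its Appendix 2 were added in version 2. Neither mentions somnolence, the seizure scope or a decision to leave out drop attack.

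**The concern.** A group labelled cataplexy and potential cataplexy should contain everything the plan calls cataplexy. As written it does not, so two adjacent safety tables can disagree about the same subject.

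The missing somnolence summary matters because somnolence bears on the choice of dose. Protocol Section 9.4.4 reports from the dose-finding study that "the rate of AEs of somnolence also increased with increasing dose level", and Section 7.2 says the trial should show efficacy at doses without meaningful morning sleepiness. A reader of the safety report will want, for each dose and for placebo, the number of subjects with any somnolence-type event. The SAP does not produce that number.

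**Working it through.** The documents give no event rates and the plan states no figure to reproduce. The check compares the lists and then asks what each table can count.

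**1. Membership.**

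| Term | SAP narrow cataplexy rule | SAP Appendix 2 (25 terms) | Protocol query (18 items) |
|---|---|---|---|
| Cataplexy | yes | yes | yes |
| Drop attack | yes | no | yes ("hypotonia, drop attacks, slurred speech, diplopia, falls") |

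One of the two narrow terms is absent from the list meant to cover both. The two groups cannot have been intended as separate, because cataplexy itself is in Appendix 2.

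A word-for-word comparison finds seven protocol items that are not in Appendix 2: drop attack, slurred speech, fall, convulsion, atypical migraine, decreased consciousness and lipothymia. This count overstates the gap. Falls and seizures have their own SAP rows, and some of the others may be covered under a different coded name. Drop attack is different: the SAP uses it as a preferred term in the same section, so wording does not explain its absence.

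**2. Effect on the counts.** Let C, D, A and F be the sets of subjects with, respectively, the term cataplexy, the term drop attack, any of the other 25 − 1 = 24 Appendix 2 terms, and any flagged event.

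- Narrow group = C ∪ D.
- Broader group as written = C ∪ A ∪ F.
- Broader group as its label implies = C ∪ D ∪ A ∪ F.
- Shortfall = number of subjects in D who are in none of C, A or F.

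Each subject whose only qualifying event is an unflagged drop attack therefore adds 1 to the narrow count and 0 to the broader one. The narrow count exceeds the broader one only if such subjects outnumber those who are in A or F but in neither C nor D.

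**3. Somnolence.** The protocol requires one grouped summary; none of the SAP's five groups is that summary. The general tables in SAP Section 3.6.3 count a subject once per preferred term and once per system organ class. If the relevant terms have n₁, …, nₖ subjects in an arm, the number with at least one lies between the largest nᵢ and the sum of the nᵢ (or the arm size, if smaller). The single-term rows do not fix it within that range. A system organ class row mixes in unrelated terms, so it does not give the number either.

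**4. Seizures.** The protocol's narrow-and-broad scope is written into the query that selects events for adjudication. It reaches the tables because Section 9.7.1.8.2 says the cataplexy-or-seizure query will be summarised, and the protocol defines no other such query. The SAP row uses narrow terms only. The mismatch rests on that inference.

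**5. A separate item.** Protocol Section 9.7.1.8.5 tabulates maximum QTcF above 450, 480 and 500 ms. SAP Section 3.6.6 keeps 450 and 500 and leaves out 480.

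**The case against.** Drop attacks are not lost. They appear in the narrow cataplexy table by system organ class and preferred term, and in the general tables. Sites are told to complete a cataplexy questionnaire for anyone who reports one, the event goes to blinded adjudication, and the adjudicated results are reported separately. A flag also brings the event into the broader group. Placing the broader rule directly after the narrow one suggests a union was intended. All of this stands, and it makes the gap a drafting slip with a limited effect. It does not repair the rule: the flag depends on judgement case by case, and a term list exists to avoid that.

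On somnolence, the term itself will be shown by treatment group, and the diary rating of morning sleepiness is analysed against placebo. The SAP states no conflicting rule, so this is an omission. The table shells are in a separate document and might include such a table, but a group with no term list in the SAP is not prespecified there. Neither the single-term rows nor the diary rating gives the grouped count.

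On seizures, a narrow-only table is a reasonable choice in itself, and Appendix 2 tabulates several of the query's other terms, such as loss of consciousness, syncope and myoclonus. That part is therefore secondary.

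Two stronger readings are tempting. A reader might infer that one or two drop attacks would make the narrow row larger than the broader one. The documents do not support this: the broader group has 24 other terms plus flagged events, and no rates are given. A reader might also infer that the protocol singles these events out as class risks. It gives no such rationale; its revision history says seizures were added to adjudication as symptoms of cataplexy.

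**Conclusion.** Two points hold.

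- The broader cataplexy group does not contain the narrow one. It falls short by exactly the number of subjects whose only qualifying event is an unflagged drop attack. That number cannot be estimated from the documents and may be zero.
- A grouped somnolence summary that the protocol requires is missing from the SAP and is not declared as a change. The general tables cannot replace it.

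The seizure scope is a weaker, secondary mismatch, because it depends on carrying the adjudication query's scope over to the summary tables. The QTcF difference is real but is not an adverse-event grouping and should be handled separately.

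SAP Section 3.6 makes the safety analyses descriptive, with no hypothesis tests, so type I error and power are unaffected. What changes is whether the safety tables agree with each other and are complete against the protocol. The corrections should be made before the safety tables are produced.

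**What to change.** 1. Add drop attack to SAP Appendix 2, or define the broader group as Appendix 2 plus both cataplexy preferred terms plus flagged events.
2. Add a somnolence and related events group to SAP Section 3.6.3.1, with its term list fixed in an appendix. Report subjects with any such event by treatment group, for Period 1 and for 12-month lemborexant exposure, as for the other groups.
3. Secondary: keep the narrow seizure row and add a narrow-plus-broad row, or record the change and its reason in SAP Section 5.
4. Separately, reconcile the QTcF category above 480 ms between protocol Section 9.7.1.8.5 and SAP Section 3.6.6.

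The cost is one added term, one term list with its tables, one further seizure row and one QTcF row. No new data are needed: the events are coded and the ECGs measured under the existing plan.

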3.6.3.2 Subgroup Analysis of TEAE

Subgroup summaries will be presented for the following summary tables. These summaries will be repeated for the Period 1 (Safety Analysis Set) and 12-month LEM exposure (On-Treatment Safety Analysis Set) separately.

- Overview table of TEAEs, including number of subjects with TEAEs, treatment-related TEAEs, severe TEAEs, treatment-emergent serious AEs (TESAEs), deaths, TEAEs leading to study drug withdrawal
- Incidence of TEAEs by SOC and PT
- Incidence of TESAEs by SOC and PT

The following demographic and baseline information will be used in the subgroup summary:

- Age group 1 (<65, 65 to <75, and ≥75 years old)
- Age group 2 (<65 and ≥65 years old)
- Sex (male and female)
- Race (white, black, Asian, and other)
- Region (North America, Europe and New Zealand, Asia)
- BMI (<25, 25 to 30, >30 kg/m²)

Percentages will be based on the total number of subjects in the relevant treatment group. A subject with 2 or more TEAEs with the same PT (or SOC) will be counted only once for that PT (or SOC).

3.6.4 Laboratory Values

Laboratory results will be summarized using Système International (SI) units, as appropriate. With the exception of urinalysis, all quantitative parameters listed in [protocol Section 9.5.1.5.3 Laboratory Measurements](#), the actual value and the change from Study Baseline will be summarized at each scheduled visit using descriptive statistics by treatment group. The change from Study Baseline/Treatment Period 2 Baseline (as appropriate) will also be repeated for the 12-month LEM exposure (On-Treatment Safety Analysis Set), summarized by treatment group and duration of exposure.

For urinalysis, the actual and the change from baseline of pH and specific gravity will be summarized at each visit by treatment group. Analysis of changes from baseline will be based on the number of subjects with both nonmissing baseline and relevant postbaseline results.

Laboratory test results will be assigned a low, normal, high (LNH) classification according to whether the value was below (L), within (N), or above (H) the laboratory parameter's reference range. Shifts from Study Baseline (LNH) to each scheduled visit will be provided by treatment group for each laboratory parameter based on Safety Analysis Set. The shift tables will also be repeated for the 12-month LEM exposure (On-Treatment Safety Analysis Set), summarized by treatment group and duration of exposure.

The Sponsor's Grading for Laboratory Values ([Appendix 1](#)) presents the Eisai criteria that will be used to identify subjects with treatment-emergent markedly abnormal laboratory values (TEMAV). Except for phosphate, a TEMAV is determined if a postbaseline grade increases from baseline and the postbaseline grade is greater than or equal to a grade of 2. For phosphate, a TEMAV was defined as a postbaseline value with an increase from baseline to a grade of 3 or higher.

The number (percentage) of subjects with TEMAVs will be summarized by treatment group using the Safety Analysis Set. The number (percentage) of subjects with TEMAVs will be produced separately for the Period 1, up to 12-months treatment, up to 6-months treatment and On-Treatment. When displaying the incidence of TEMAVs, each subject will be counted

once in the laboratory parameter high and in the laboratory parameter low categories, as applicable.

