9.7.1.8.3 LABORATORY VALUES

Clinical laboratory values will be evaluated for each laboratory parameter by subject. Abnormal laboratory values will be identified as those outside (above or below) the normal range. Reference (normal) ranges for laboratory parameters will be included in the CSR for this study. Descriptive summary statistics (eg, mean, SD, median, minimum, maximum for continuous variables, and number and percentage for categorical variables) for the laboratory parameters and changes from Study Baseline will be evaluated by treatment group and visit. This will also be repeated for the 12-month LEM exposure (On-Treatment Safety Analysis Set), summarized by treatment group and duration of exposure. (revised per Amendment 06)

Laboratory test results will be assigned a low, normal, high (LNH) classification according to whether the value was below (L), within (N), or above (H) the laboratory parameter's reference range. Within-treatment comparisons will be based on 3 by 3 tables (shift tables) that, for a particular laboratory test, compare the Study Baseline LNH classification to the LNH classification at Month 6 by treatment group. This will also be repeated for the 12-month LEM exposure (On-Treatment Safety Analysis Set), summarized by treatment group and duration of exposure. (revised per Amendment 06)

Clinical laboratory results post-Study Baseline will be evaluated for markedly abnormal values. A laboratory test will be considered markedly abnormal if the result worsens to meet Eisai grading criteria for laboratory values limit of Grade 2 or higher. If the Grade 2 limit is missing, the Grade 1 limit will be considered. [Appendix 1](#) presents the Eisai grading criteria for laboratory values that were used to identify subjects with markedly abnormal laboratory values. For the incidence of markedly abnormal laboratory values, each subject may be counted once in the laboratory parameter value high and in the laboratory parameter low categories as applicable.

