Glucose, serum-low (hypoglycemia)	<LLN – 55 mg/dL <LLN – 3.0 mmol/L	<55 – 40 mg/dL <3.0 – 2.2 mmol/L	<40 – 30 mg/dL <2.2 – 1.7 mmol/L	<30 mg/dL <1.7 mmol/L life-threatening consequences; seizures
Phosphate, serum-low (hypophosphatemia)	<LLN – 2.5 mg/dL <LLN – 0.8 mmol/L	<2.5 – 2.0 mg/dL <0.8 – 0.6 mmol/L	<2.0 – 1.0 mg/dL <0.6 – 0.3 mmol/L	<1.0 mg/dL <0.3 mmol/L life-threatening consequences
Potassium, serum-high (hyperkalemia)	>ULN – 5.5 mmol/L	>5.5 – 6.0 mmol/L	>6.0 – 7.0 mmol/L hospitalization indicated	>7.0 mmol/L life-threatening consequences
Potassium, serum-low (hypokalemia)	<LLN – 3.0 mmol/L	<LLN – 3.0 mmol/L; symptomatic; intervention indicated	<3.0 – 2.5 mmol/L hospitalization indicated	<2.5 mmol/L life-threatening consequences
Sodium, serum-high (hypernatremia)	>ULN – 150 mmol/L	>150 – 155 mmol/L	>155 – 160 mmol/L hospitalization indicated	>160 mmol/L life-threatening consequences
Sodium, serum-low (hyponatremia)	<LLN – 130 mmol/L	N/A	<130 – 120 mmol/L	<120 mmol/L life-threatening consequences
Triglyceride, serum-high (hypertriglyceridemia)	150 – 300 mg/dL 1.71 – 3.42 mmol/L	>300 – 500 mg/dL >3.42 – 5.7 mmol/L	>500 – 1000 mg/dL >5.7 – 11.4 mmol/L	>1000 mg/dL >11.4 mmol/L life-threatening consequences
Uric acid, serum-high (hyperuricemia)	>ULN – 10 mg/dL ≤0.59 mmol/L without physiologic consequences	N/A	>ULN – 10 mg/dL ≤0.59 mmol/L with physiologic consequences	>10 mg/dL >0.59 mmol/L life-threatening consequences

ALT = alanine aminotransferase (serum glutamic pyruvic transaminase), AST = aspartate aminotransferase (serum glutamic oxaloacetic transaminase), GGT = γ -glutamyl transpeptidase, N/A = not applicable, LLN = lower limit of normal, ULN = upper limit of normal, WBC = white blood cell.

Based on Common Terminology Criteria for Adverse events (CTCAE) Version 4.0. Published: 28 May 2009 (v4.03: 14 Jun 2010).

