5 CHANGES IN THE PLANNED ANALYSES

The following major changes to the statistical methods in this analysis plan were made after Amendment 03 of the Protocol was approved.

- Additional time points (ie., Months 2, 4, 5) have been included in MMRM as covariates for the primary and key secondary analysis.
- An additional safety analysis set (ie., On-Treatment Safety Analysis Set) has been defined and the safety analysis based on the On-Treatment Safety Analysis Set has been added.

The full changes to the statistical methods in this analysis plan were made in version 2.0 of the SAP from version 1.0 are detailed in [Table 1](#) at the beginning of the SAP.

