Glucose, serum-high (hyperglycemia)	Fasting glucose value: >ULN – 160 mg/dL >ULN – 8.9 mmol/L	Fasting glucose value: >160 – 250 mg/dL >8.9 – 13.9 mmol/L	>250 – 500 mg/dL; >13.9 – 27.8 mmol/L; hospitalization indicated	>500 mg/dL; >27.8 mmol/L; life-threatening consequences
Glucose, serum-low (hypoglycemia)	<LLN – 55 mg/dL <LLN – 3.0 mmol/L	<55 – 40 mg/dL <3.0 – 2.2 mmol/L	<40 – 30 mg/dL <2.2 – 1.7 mmol/L	<30 mg/dL <1.7 mmol/L life-threatening consequences; seizures
Phosphate, serum-low	<LLN – 2.5 mg/dL	<2.5 – 2.0 mg/dL	<2.0 – 1.0 mg/dL	<1.0 mg/dL

	Grade 1	Grade 2	Grade 3	Grade 4
(hypophosphatemia)	<LLN – 0.8 mmol/L	<0.8 – 0.6 mmol/L	<0.6 – 0.3 mmol/L	<0.3 mmol/L life-threatening consequences
Potassium, serum-high (hyperkalemia)	>ULN – 5.5 mmol/L	>5.5 – 6.0 mmol/L	>6.0 – 7.0 mmol/L hospitalization indicated	>7.0 mmol/L life-threatening consequences
Potassium, serum-low (hypokalemia)	<LLN – 3.0 mmol/L	<LLN – 3.0 mmol/L; symptomatic; intervention indicated	<3.0 – 2.5 mmol/L hospitalization indicated	<2.5 mmol/L life-threatening consequences
Sodium, serum-high (hypernatremia)	>ULN – 150 mmol/L	>150 – 155 mmol/L	>155 – 160 mmol/L hospitalization indicated	>160 mmol/L life-threatening consequences
Sodium, serum-low (hyponatremia)	<LLN – 130 mmol/L	N/A	<130 – 120 mmol/L	<120 mmol/L life-threatening consequences
Triglyceride, serum-high (hypertriglyceridemia)	150 – 300 mg/dL 1.71 – 3.42 mmol/L	>300 – 500 mg/dL >3.42 – 5.7 mmol/L	>500 – 1000 mg/dL >5.7 – 11.4 mmol/L	>1000 mg/dL >11.4 mmol/L life-threatening consequences
Uric acid, serum-high (hyperuricemia)	>ULN – 10 mg/dL ≤0.59 mmol/L without physiologic consequences	N/A	>ULN – 10 mg/dL ≤0.59 mmol/L with physiologic consequences	>10 mg/dL >0.59 mmol/L life-threatening consequences

ALT = alanine aminotransferase (serum glutamic pyruvic transaminase), AST = aspartate aminotransferase (serum glutamic oxaloacetic transaminase), GGT = γ -glutamyl transpeptidase, N/A = not applicable, LLN = lower limit of normal, ULN = upper limit of normal, WBC = white blood cell.

Based on Common Terminology Criteria for Adverse events (CTCAE) Version 4.0. Published: May 28, 2009 (v4.03: June 14, 2010).

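### Protocol 9.7.1.8.3 and SAP 3.6.4 give conflicting rules for a markedly abnormal laboratory value, so low sodium, phosphate and uric acid are counted differently

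*SAP*

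**What the plan says.** Protocol 9.7.1.8.3 makes Grade 2 the lowest grade that counts: "A laboratory test will be considered markedly abnormal if the result worsens to meet Eisai grading criteria for laboratory values limit of Grade 2 or" (the sentence then takes in every grade above that). It adds a fallback for rows of the grading table that have no Grade 2: "If the Grade 2 limit is missing, the Grade 1 limit will be considered". No analyte is exempted.

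SAP 3.6.4 counts treatment-emergent markedly abnormal values (TEMAVs, the SAP's term). Its general rule, with a threshold of Grade 2, is "Except for phosphate, a TEMAV is determined if a postbaseline grade increases from baseline and the postbaseline grade is greater than or equal to a" (quoted up to the threshold). Phosphate has its own sentence: "For phosphate, a TEMAV was defined as a postbaseline value with an increase from baseline to a grade of 3 or higher". The section contains no Grade 1 fallback.

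Appendix 1 gives the same grade limits in both documents. Grade 2 is not applicable in two rows only, low sodium and uric acid. Across Grades 1 to 3 the low-sodium row reads "<LLN – 130 mmol/L N/A <130 – 120 mmol/L". Uric acid Grades 1 and 3 cover the same numeric range, and Grade 1 is marked "without physiologic consequences". Low-potassium Grade 2 repeats the Grade 1 range and adds "symptomatic; intervention indicated".

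SAP section 5 opens with "The following major changes to the statistical methods in this analysis plan were made after Amendment 03 of the Protocol was approved". It lists two items, the added MMRM time points and the On-Treatment Safety Analysis Set. Neither concerns laboratory grading.

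**The concern.** The fallback serves exactly the two rows without a Grade 2, and the SAP drops it. The SAP also raises the phosphate threshold by one grade. The same result in the same subject can therefore be markedly abnormal under one document and not under the other.

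The count is reported. SAP 3.6.1 includes TEMAVs among the summaries for Period 1 (placebo, LEM5, LEM10) and for 12-month lemborexant exposure, and SAP 3.6.4.1 repeats them by subgroup. SAP section 3 plans three database locks and unblinds the sponsor once all subjects have completed Period 1. If the conflict is still open at that point, it will be settled by staff who can see treatment.

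**Working it through.** No sample size or power figure is involved. The check applies each rule to the shared grading table.

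**Inputs.** The grade limits are from Appendix 1 (both documents) and the rules are from Protocol 9.7.1.8.3 and SAP 3.6.4. Protocol 9.5.1.5.3 (Table 1) confirms that sodium, potassium, phosphorus and uric acid are measured. The documents give no LLN or ULN, so these ranges are assumed: sodium LLN 133 to 137 mmol/L, phosphate LLN 2.5 to 2.7 mg/dL, uric acid ULN 6 to 8.5 mg/dL, potassium LLN 3.4 to 3.6 mmol/L. Baseline is taken as Grade 0.

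**Rules as cut-offs.** A result counts if its grade has risen from baseline and is at least c.
- Protocol: c = 2 where a Grade 2 limit exists, otherwise c = 1.
- SAP: c = 2, except c = 3 for phosphate.

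The documents disagree on grades from the protocol's c up to, but not including, the SAP's c.

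| Abnormality | Protocol c | SAP c | Disputed grade | Disputed range |
|---|---|---|---|---|
| Low sodium | 1 | 2 | 1 | 130 mmol/L to <LLN |
| Phosphate | 2 | 3 | 2 | 2.0 to <2.5 mg/dL (0.6 to <0.8 mmol/L) |
| Uric acid | 1 | 2 | 1 | >ULN to 10 mg/dL, if no physiologic consequences |
| All other rows | 2 | 2 | none | none |

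**Test values.**
- Sodium, LLN 135: 134 and 130 count under the protocol and not under the SAP; 129 counts under both.
- Phosphate, LLN 2.6: 2.5 counts under neither; 2.4 and 2.0 count under the protocol only; 1.9 counts under both.
- Uric acid, ULN 7: 7.5 and 10 count under the protocol. Under the SAP they are Grade 1 (not counted) or Grade 3 (counted), and the value alone cannot say which. 10.1 counts under both.

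The pattern was the same at every assumed LLN and ULN. Because the SAP's c is never below the protocol's, the SAP count for a row can equal the protocol count but cannot exceed it.

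**Potassium.** Both documents have c = 2. With LLN 3.5, values of 3.2 and 3.0 mmol/L are Grade 1 or Grade 2 depending on symptoms or intervention, so they are undetermined under both rules; 2.9 counts under both. This is an ambiguity within each document and does not set one against the other.

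**The case against.** The strongest reply is that little is lost. SAP 3.6.4 also requires low/normal/high shift tables from Study Baseline to each scheduled visit for each parameter, repeated for 12-month exposure, with descriptive values and changes. From a normal baseline, sodium of 134 (LLN 135) and uric acid of 7.5 (ULN 7) appear there as shifts, and so does phosphate of 2.4 if it is below the laboratory's LLN. That stands, and it limits the consequence. The shift tables do not settle which TEMAV count is right, and with a phosphate LLN above 2.5 mg/dL they do not separate 2.0 to <2.5 mg/dL from milder low values.

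The SAP's narrower definition is also not an error in itself. The phosphate exception looks deliberate, and the protocol's fallback would label a sodium of 134 markedly abnormal when LLN is 135. That too stands. The defect is that two rules are in force and the departure is not declared; neither rule is shown to be the wrong one.

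SAP section 7 places derivation rules in separate documents, which may cover the grades that depend on symptoms. They could settle potassium and uric acid programming, but would not reconcile two written definitions.

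A reader might infer more than the documents support:
- That potassium counts also differ between protocol and SAP. They do not; the overlap is the same in both.
- That sodium differs in both directions. High sodium has a Grade 2 limit, so the rules agree.
- That silence in SAP Table 1 shows an undeclared change. That table records changes from SAP version 1.0 to 2.0, not departures from the protocol. Section 5 is the relevant place.
- That the treatment comparison is biased. Either rule applies equally to all arms, SAP 3.6 plans no safety hypothesis tests, and nothing shows an effect in one arm only.

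**Conclusion.** The conflict is real and limited to three abnormalities: low sodium, phosphate and uric acid. It follows from the wording of the two rules and an identical grading table; only the worked values rest on assumed normal limits. The direction is known, since the SAP count is the same or lower. The number of subjects affected cannot be computed, because the documents give neither laboratory distributions nor normal limits. The effect is confined to descriptive safety tables and leaves the efficacy inference untouched. It still merits correction, because the reported incidence in a placebo-compared table depends on which document is followed. The low-potassium overlap is a secondary point about an incomplete derivation.

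**What to change.** Reconcile Protocol 9.7.1.8.3 and SAP 3.6.4 before the first database lock, in one of two ways.

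1. Restore the protocol rule in SAP 3.6.4: Grade 2 or above, the Grade 1 limit where Grade 2 is not applicable, and no phosphate exception. This also resolves uric acid, since everything above ULN then counts if it has worsened.
2. Keep the SAP rule, declare it in section 5 with a reason, and tabulate both counts for low sodium, phosphate and uric acid. The SAP must then also say how uric acid between ULN and 10 mg/dL is handled when only the laboratory value is available.

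Under either option, add one numeric convention for low potassium that says whether results from 3.0 mmol/L to <LLN count as a TEMAV.

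The cost is SAP wording and, at most, a few table rows, with no new data. The downside is more low-grade flags in the safety tables.
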